## **3.2 END OF STUDY AND LENGTH OF STUDY**

The end of this study is defined as the time when both of the following criteria are met:

- All enrolled patients with FL have *been followed for at least 90 days after they have completed or discontinued study treatment (including induction treatment and maintenance treatment as applicable)*.
- All enrolled patients with DLBCL have been followed for at least 1 year after they have completed or discontinued study treatment (including induction treatment and consolidation treatment as applicable).

The total length of the study, from screening of the first patient to the end of the study, is expected to be approximately 5 years.

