#### **5.3.1 Adverse Event Reporting Period**

Investigators will seek information on adverse events at each patient contact. All adverse events, whether reported by the patient or noted by study personnel, will be recorded in the patient’s medical record and on the Adverse Event eCRF.

**After informed consent has been obtained but prior to initiation of study treatment**, only serious adverse events caused by a protocol-mandated intervention (e.g., invasive procedures such as biopsies, discontinuation of medications) should be reported (see Section 5.4.2 for instructions for reporting serious adverse events).

**After initiation of study treatment**, all adverse events will be reported until 90 days after the last dose of study treatment. After this period, the investigator should report any serious adverse events that are believed to be related to prior study treatment *and events of second malignancies for patients who received obinutuzumab* (see Section 5.6).

An exception is *for the FL patients, where* Grade 3 and 4 infections (both related and unrelated) should be reported until up to 2 years after the last dose of *obinutuzumab*.

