## **5.6 ADVERSE EVENTS THAT OCCUR AFTER THE ADVERSE EVENT REPORTING PERIOD**

The Sponsor should be notified if the investigator becomes aware of any serious adverse event that occurs after the end of the adverse event reporting period (defined as 90 days after the last dose of study treatment), if the event is believed to be related to prior study treatment. *The sponsor should also be notified of events of second malignancies after the end of the adverse event reporting period for patients who received obinutuzumab.*

An exception is *for patients receiving obinutuzumab, where Grade 3–4 infections (both related and unrelated) should be reported until up to 2 years after the last dose of study treatment.*

The investigator should report these events directly to the Sponsor or its designee, either by faxing or by scanning and emailing the Serious Adverse Event/Adverse Event of Special Interest Reporting *Form* using the fax number or email address provided to investigators.

During survival follow-up, deaths attributed to progression of lymphoma should be recorded only on the Study Completion/Early Discontinuation eCRF.

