### Schedule of Assessments for Patients with Follicular Lymphoma (cont.)

---

- aa After informed consent has been obtained but prior to initiation of study treatment, only serious adverse events caused by a protocol-mandated intervention should be reported. After initiation of study treatment, all adverse events will be reported until 90 days after the last dose of study treatment. After this period, the Sponsor should be notified if the investigator becomes aware of any serious adverse event that is believed to be related to prior study treatment (see Section 5.6). An exception is made for Grade 3 and 4 infections (related and unrelated), which should be reported until up to 2 years after the last dose of *obinutuzumab*. The investigator should follow each adverse event until the event has resolved to baseline grade or better, the event is assessed as stable by the investigator, the patient is lost to follow-up, or the patient withdraws consent. Every effort should be made to follow all serious adverse events considered to be related to any of the study treatment components or trial-related procedures until a final outcome can be reported.
- bb The screening PET-CT scan must be performed within 35 days prior to Day 1 of Cycle 1.
- cc Perform only for patients who have received at least two cycles of induction treatment.
- dd If PET-CT scan is positive at EOI, perform at 12 months after initiation of induction treatment, within 14 days prior to treatment administration.
- ee Includes CT scan of the neck (if clinically indicated), chest, abdomen, and pelvis. If contrast is medically contraindicated (e.g., patients with contrast allergy or impaired renal clearance), MRI scans of the chest, abdomen, and pelvis (and neck, if clinically indicated) and a non-contrast CT scan of the chest may be performed. Combined PET/CT scanners may be used to collect diagnostic CT scans, but only according to the technical guidelines in the imaging manual. The screening CT scan must be performed within 35 days prior to Day 1 of Cycle 1.
- ff Perform *within 7 days prior to Day 1 of Cycle 3* and at 12, 18, and 24 months after initiation of induction treatment.
- gg Perform only if not done within the previous 3 months.
- hh Perform every 6 months.
- ii Bone marrow biopsy and aspirate must be performed within approximately 3 months prior to Day 1 of Cycle 1.

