**Appendix 3**  
**Pharmacokinetic and Immunogenicity Sampling Schedule for Obinutuzumab, Polatuzumab Vedotin, and Lenalidomide in Relapsed or Refractory FL Patients (cont.)**

Study Visit	Serum Obinutuzumab PK Sample a,b	Serum Polatuzumab Vedotin PK Sample for Total Antibody a,b	Plasma Polatuzumab Vedotin PK Sample for Antibody Conjugated MMAE and Unconjugated MMAE a	Plasma Lenalidomide PK Sample a	Serum Obinutuzumab HAAA Sample a	Serum Polatuzumab Vedotin ATA Sample a
Treatment discontinuation	Anytime during visit	Anytime during visit		–	Anytime during visit	Anytime during visit
20 ±30 days after last dose of obinutuzumab and polatuzumab (as appropriate for sample)	Anytime during visit	Anytime during visit	–	–	Anytime during visit	Anytime during visit
1-2 years after last dose of obinutuzumab	Anytime during visit (if patient in clinic)	Anytime during visit	–	–	Anytime during visit (if patient in clinic)	Anytime during visit (if patient in clinic)

### Appendix 3

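### The FL end-of-study rule can close the study before the 2-year Grade 3-4 infection window is complete, so late infections may be incompletely captured; separately, that window has two different start points

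*Combined protocol and SAP*

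**What the plan says.** Section 3.2 ends the study when two criteria are both met. FL patients must have "been followed for at least 90 days after they have completed or discontinued study treatment", and the second criterion reads "All enrolled patients with DLBCL have been followed for at least 1 year after they have completed or discontinued study treatment". Total length "is expected to be approximately 5 years". Appendix 1 footnote d gives a different definition: the study ends when every patient has finished or stopped treatment, or when the Sponsor ends it. It sets no follow-up minimum.

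For FL patients, Section 5.3.1 says that "Grade 3 and 4 infections (both related and unrelated) should be reported until up to 2 years after the last dose of" obinutuzumab, and Appendix 1 footnote aa repeats this anchor. Section 5.6 says that such infections "should be reported until up to 2 years after the last dose of study treatment".

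Appendix 3 has an FL sampling row labelled "1-2 years after last dose of obinutuzumab". Three of its four samples (obinutuzumab PK, HAHA and ATA) are taken only if the patient happens to be in clinic. The total-antibody sample carries no such condition.

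Under Section 3.1.6, post-treatment visits stop at progression, new anti-lymphoma therapy or end of study. After progression, only survival status and new treatment are followed. Section 6.5 summarizes all adverse events from first treatment onward, with no reference to time at risk.

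**The concern.** Infection is an identified obinutuzumab risk (Section 5.1.1) and a selected adverse event (Section 5.2.5). Section 5.1.1.5 states that serious infections can occur after therapy is completed and that fatal ones have been reported. The 2-year window exists to catch these events, but the end-of-study rule does not protect it.

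Section 5.3.1 relies on patient contacts to elicit adverse events. Once the study closes, no contacts are scheduled, and reports under Section 5.6 go to the Sponsor by fax or email form. The plan does not say how those reports reach the study database or the Section 6.5 tables. A crude proportion would then pool patients observed for about 3 months with patients observed for 24 months, and could read as a low late-infection frequency.

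**Working it through.** **The plan's own figure.** The 5-year length cannot be reproduced, because no accrual period is given. Working backwards, with 28 days of screening and 902 days from first dose to FL closure (derived below), 1826 − 28 − 902 = 896 days. That is about 29 months of accrual if the FL criterion is the one that closes the study.

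**Timeline for an FL patient completing maintenance.** Day 1 is Cycle 1 Day 1; cycles and months are 28 days (Table 5 notes); no delays.

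- Cycle 6 Day 1: 1 + 5×28 = Day 141.
- Maintenance Month 1, 8 weeks later (Section 3.1.2.2): 141 + 56 = Day 197.
- Last planned obinutuzumab dose, Month 23 Day 1 (Table 5): 197 + 22×28 = Day 813.
- Earliest date the FL criterion is met: 813 + 90 = Day 903.
- End of the 2-year window: 813 + 730 = Day 1543.
- Window left without visits: 1543 − 903 = 640 days; 640/730 = 88%.

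If the 90 days run from the end of Month 24 (197 + 24×28 = Day 869), closure is Day 959 and the gap is 584 days (80%). Under Appendix 1 footnote d, the study could end with the last treatment, leaving that patient's whole window without visits.

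**Does the DLBCL criterion keep the study open?** The last DLBCL lenalidomide dose is Month 6 Day 21: 197 + 5×28 + 20 = Day 357. Adding 365 gives Day 722. With equal start dates this falls before Day 903. The DLBCL criterion binds only if the last DLBCL patient starts more than 903 − 722 = 181 days after the last FL patient. It covers the full FL window only with a lag of at least 1543 − 722 = 821 days (27 months).

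**Coverage across FL patients.** Assumptions not in the documents: uniform FL accrual over A days, all FL patients complete maintenance, the FL criterion closes the study, and visits are not stopped by progression or new therapy. A patient enrolled u days before the last one is observed for min(730, 90 + u) days. The share with a full window is max(0, (A − 640)/A).

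| Accrual | Full 2-year window | Mean days observed | Mean share of window |
|---|---|---|---|
| 365 days (12 months) | 0% | 272 | 37% |
| 548 days (18 months) | 0% | 364 | 50% |
| 730 days (24 months) | 12% | 449 | 62% |
| 896 days (29 months, implied by 5 years) | 29% | 501 | 69% |
| 1096 days (36 months) | 42% | 543 | 74% |

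**The two anchors.** For a maintenance completer they coincide: lenalidomide ends at Month 12 Day 21 (197 + 11×28 + 20 = Day 525), before obinutuzumab on Day 813. They differ by 20 days if treatment stops after Cycle 6, and by up to 28 + 20 = 48 days if it stops during maintenance. Section 5.1.7 allows one drug to stop while the others continue. In the extreme, with obinutuzumab stopped after Cycle 1 Day 1 and lenalidomide run to Month 12, they differ by 525 − 1 = 524 days. Because obinutuzumab is itself a study treatment, the Section 5.6 anchor is never the earlier of the two.

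**The case against.** The best defence is that 90 days is a floor, that both criteria must be met, and that Section 5.6 exists for events after the routine reporting period. Section 5.6 gives a direct route to the Sponsor and does not say that the duty lapses at closure. Relying on direct reports is a legitimate choice in a single-arm Phase Ib/II study of about 40 FL expansion patients, with no 2-year infection rate among its endpoints. All of that stands. It means that incomplete capture is a risk, not a certainty.

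Four stronger readings are tempting, and the documents do not support them:

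- **That late infection rates will be understated.** Earlier enrollees and early discontinuers have more calendar time, late DLBCL accrual may extend the study, and Section 5.6 reporting continues.
- **That the two anchors contribute to understatement.** The Section 5.6 window is the same or longer, so the mismatch produces inconsistency only.
- **That 88% of the window is typically lost.** That figure is the worst case under Section 3.2, for the last FL completer.
- **That Section 3.2 contradicts a firm late sampling schedule.** Three of the four samples are opportunistic.

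The defence does not resolve the conflicting end-of-study definitions, the undefined route from post-closure reports to the tables, or the unequal observation times that a crude summary would ignore.

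**Conclusion.** The point holds as a reconciliation and analysis issue. The current text can close the study before the FL infection window and the 1-2 year samples are complete. The gap is up to 640 of 730 days for the last FL completer under Section 3.2, and potentially the whole window under Appendix 1 footnote d. Under the stated accrual assumptions, between 0% and 42% of FL patients would have a full window, and 29% at the accrual implied by a 5-year study. These shares are illustrative, because the documents give no accrual period or completion rate. Late infections may therefore be incompletely captured, and crude Section 6.5 summaries may understate them.

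The anchor mismatch is a separate inconsistency, with no effect for maintenance completers. The primary endpoint, complete response at end of induction, is unaffected.

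**What to change.** 1. In Section 5.6, start the Grade 3-4 infection window from the last obinutuzumab dose, as Section 5.3.1 and Appendix 1 footnote aa do.
2. Reconcile Section 3.2, Appendix 1 footnote d, Sections 5.3.1 and 5.6, and Appendix 3, so that there is one end-of-study definition and the fate of the 2-year window and late samples after closure is explicit. State how infections reported after closure enter the database.
3. In Section 6.5, report FL Grade 3-4 infections within the 90-day period as a proportion, noting patients not followed that long (Section 4.6.1 ends follow-up when consent is withdrawn). Report later ones as a person-time rate or a censored cumulative incidence. End time at risk when active adverse event ascertainment ends: progression, new therapy, withdrawal or study closure. List infections reported after that point separately, so that events and time at risk match.

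The cost is wording changes and one extra table. The late rates will be imprecise. Longer follow-up is not needed for this. Making the FL criterion 2 years after obinutuzumab would add 640 days (about 1.75 years), taking a 5-year study to about 6.75 years at the implied accrual.

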### **3.3 RATIONALE FOR STUDY DESIGN**

#### **3.3.1 Rationale for Patient Population**

As discussed in Section 1.1.1, despite significant therapeutic progress with the use of chemoimmunotherapy as first-line treatment, FL remains essentially an incurable disease. Patients invariably relapse, and subsequent active and well-tolerated agents are needed. DLBCL can be cured in > 50% of cases; however, up to one-third of patients have refractory disease of relapse after treatment. Success rates with salvage therapy and autologous transplantation are poor, highlighting the urgent need for novel therapeutic approaches for these patients.

On the basis of a compelling biologic and clinical rationale, as presented in Section 1.4, the addition of polatuzumab vedotin to obinutuzumab *or rituximab* and lenalidomide is a promising approach to expand the number of patients with R/R FL and DLBCL who achieve remission and to prolong response duration in these patients.

The study will include an initial dose-escalation phase followed by an expansion phase. The objective of the dose-escalation phase is to define the RP2D for lenalidomide and the RP2D dose for polatuzumab vedotin when given with obinutuzumab *in patients with R/R FL and the RP2D for lenalidomide when given in combination with polatuzumab at 1.8 mg/kg and rituximab at 375 mg/m^2 in patients with R/R DLBCL*. Although the DLT assessment window is the first cycle of treatment, long-term or cumulative toxicities will also be assessed and considered for the dose definition.

#### **3.3.2 Rationale for the Triplet Combination**

This study combines treatments with different MOA that have demonstrated clinical activity against B-cell lymphoma. Refer to [Appendix 11](#) for descriptions of clinical studies that use the study drugs as single or doublet treatment.

As discussed in Section 1.4, there is a strong MOA and clinical rationale to expect an improved benefit-risk profile with the triplet combination of obinutuzumab *or rituximab*, polatuzumab vedotin, and lenalidomide over standard immunochemotherapy regimens. The hypothesis is that this novel triplet regimen may have the potential to extend treatment-free remissions and decrease toxicity by improving upon individual agents in the current standard of care. Overlapping toxicities are anticipated and expected to be manageable in the clinical setting (see Section 5.1.5).

As discussed in Section 1.4, the development of obinutuzumab in B-cell malignancies is based on the hypothesis that obinutuzumab will be a superior anti-CD20 agent compared to rituximab *in patients with FL*. This has been demonstrated in CLL ([Goede et al. 2014](#)) and *has been studied in two additional Phase III studies in DLBCL and FL*.

*Study BO21223 investigated obinutuzumab plus chemotherapy (G-benda, G-CVP, G-CHOP) compared with rituximab plus chemotherapy, followed by obinutuzumab or*

*rituximab maintenance in patients with previously untreated iNHL (FL cohort, n =1202) and demonstrated positive results, showing a significant improvement in PFS in the obinutuzumab chemotherapy arm.*

*Study BO21005, investigated G-CHOP compared with R-CHOP in patients with previously untreated DLBCL and this study did not meet its primary endpoint of PFS at final analysis.*

*On the basis of the results of these Phase III studies evaluating obinutuzumab in combination with chemotherapy in both FL and DLBCL, patients with R/R FL in this current protocol amendment will continue to receive obinutuzumab in combination with polatuzumab vedotin and lenalidomide, while patients with R/R DLBCL will instead receive rituximab in combination with polatuzumab vedotin and lenalidomide.*

In the following sections, data generated for rituximab in combination with either polatuzumab vedotin or lenalidomide are also provided to further support the combination of an anti-CD20 antibody with polatuzumab vedotin and lenalidomide.

### **3.3.2.1 Rituximab and Polatuzumab Vedotin Combination**

During its early development, polatuzumab vedotin treatment has been investigated as a single agent and in combination with rituximab. On the basis of available Phase I and II data (see Section 3.3.3.2 and Appendix 11), polatuzumab vedotin as a single agent and combined with rituximab has shown clinical activity in heavily pretreated patients with R/R B-cell lymphoma (Palanca-Wessels et al. 2012; Morschhauser et al. 2014a). In both studies, patients received rituximab 375 mg/m^2 and polatuzumab vedotin up to 2.4 mg/kg Q3W for up to 1 year, progression, or unacceptable toxicity. *The ongoing Study GO27834 has also shown preliminary safety and efficacy results evaluating the combination of rituximab and polatuzumab vedotin 1.8 mg/kg.*

### **3.3.2.2 Obinutuzumab and Polatuzumab Vedotin Combination**

The combination of obinutuzumab with polatuzumab vedotin is being evaluated in several ongoing studies (see Table 11), including two Phase Ib/II trials in patients with R/R FL. *Preliminary results from these studies show safety and efficacy at the polatuzumab vedotin 1.8-mg/kg dose level when combined with obinutuzumab, every 3 weeks for 6–8 cycles as described in Section 1.3.2.*

### **3.3.2.3 Rituximab and Lenalidomide Combination**

The thalidomide analogue lenalidomide is currently approved for the treatment of multiple myeloma, deletion 5q myelodysplastic syndromes, and MCL as Revlimid. Nonclinical studies demonstrated that T-cell immune synapse dysfunction in FL can be restored with lenalidomide (Ramsay et al. 2009). In addition, lenalidomide has been shown to reduce T regulatory cells and activate CD8 T cells (Kater et al. 2014). E3 ligase protein cereblon (encoded by the *CRBN* gene) is the molecular target of lenalidomide. Lenalidomide binding to CRBN mediated its direct anti-tumor effects and

is also required for T-cell production of interleukin-2 and tumor necrosis factor  $\alpha$  (Lopez-Girona et al. 2012).

In nonclinical studies, lenalidomide combined with rituximab resulted in anti-tumor effects via increased NK-cell function, enhanced antibody-dependent cell-mediated cytotoxicity, and improved NK cell-mediated synapse formation (Wu et al. 2008; Zhang et al. 2009).

Although lenalidomide has not been approved for the treatment of R/R FL and DLBCL, clinical activity has been demonstrated in the treatment of both R/R indolent and aggressive B-cell lymphoma with lenalidomide as a single agent (Wiernik et al. 2008; Witzig et al. 2009, 2011) or in combination with rituximab (Zinzani et al. 2011, 2013; Leonard et al. 2012; Tuscano et al. 2014; Wang et al. 2013) or obinutuzumab (Morschhauser et al. 2014b) (see Appendix 11).

#### **3.3.2.4 Obinutuzumab and Lenalidomide Combination**

Because the combination of lenalidomide and rituximab has been shown to be synergistic in nonclinical models and in patients with relapsed and first-line FL, replacing rituximab with obinutuzumab in combination with lenalidomide might be even more efficient than the lenalidomide and rituximab combination.

The combination of obinutuzumab with lenalidomide has been evaluated in nonclinical studies using the MCL Z138 xenograft model in SCID-beige mice. Results from these studies demonstrated greater anti-tumor efficacy than either single agent and superior activity to the combination of lenalidomide with rituximab (data available upon request [RDR 1064289]).

The combination of obinutuzumab with lenalidomide is currently being investigated in an ongoing Phase Ib/II study sponsored by the Lymphoma Academic Research Organisation (GALEN study) as induction and maintenance treatment in patients with R/R FL and aggressive lymphoma (DLBCL and MCL). The recommended dose of lenalidomide was established at 20 mg/day on the basis of an increased incidence of Grade 3 or 4 neutropenia between Cycles 2 and 6 at the next higher dose of 25 mg/day (Morschhauser et al. 2014). The most common adverse events observed during the dose-escalation phase (all grades,  $\geq 20\%$  patients) were neutropenia (10/19; 53%), constipation (10/19; 53%) asthenia (7/19; 37%), upper respiratory tract infection (7/19; 37%), rash/cutaneous eruption (5/19; 26%), cough (5/19; 26%), diarrhea (4/19; 21%), and fever (4/19, 21%). Grade 3/4 adverse events occurring in  $\geq 2$  patients only consisted of neutropenia (8/19; 42%). IRRs occurred in 3 patients and did not exceed Grade 2. Preliminary efficacy data available from the dose-escalation phase of the study are encouraging, with an overall response according to Cheson et al. 1999 criteria of 68% (13 of 19 evaluable patients), including 7 patients with a CR; 3 patients with a CR, unconfirmed; and 3 patients with a PR (Morschhauser et al. 2014). Enrollment in the expansion phase at 20 mg/day (Phase II part) is in progress. Available preliminary

unpublished data (cutoff date: 30 September 2014) for 45 patients evaluable for safety during the induction period (Cycles 1–6) show a median of 5 induction cycles (range: 2–6 cycles) received. The following hematologic adverse events (all grades) were reported: neutropenia (17/45; 37.8%), febrile neutropenia (3/45; 6.7%), anemia (8/45; 17.8%), and thrombocytopenia (5/45; 11.1%). The most common (occurring in > 10% of patients) non-hematologic adverse events (all grades) were constipation (9/45; 20%); rash (7/45; 15.6%); cough (7/45; 15.6%); asthenia (6/45; 13.3%); and fatigue, diarrhea, and pruritus (5/45; 11.1% each).

As mentioned in Section 1.4, there is a strong rationale for enhanced activity with combination therapy as well as apparent limited additional toxicity that argues that exploration of the G+Pola+Len combination is appropriate. This novel triplet regimen may have the potential to extend treatment-free remissions and decrease toxicity by improving upon individual agents in current standard of care and incorporating a targeted chemotherapy regimen.

